10.4 Participant Mental Status

Survey questions may ask about the mental status of participants, including suicidal ideation. The CSC and site staff will receive an alert when a response suggesting possible thoughts of suicidality is submitted. Upon receipt, CSC staff will communicate with site study staff to confirm accuracy of the response and verify appropriate measures are taken to ensure participant safety.

11 Study Oversight

11.1 Monitoring Board

Oversight of data and safety is provided by a RECOVER Observational Safety Monitoring Board (OSMB) appointed by the National Heart, Lung and Blood Institute (NHLBI). A charter of the OSMB will be submitted for IRB review before starting enrollment. The OSMB will meet at least twice a year to review data on AEs, unanticipated events, patient-reported outcomes, data quality, and study recruitment as described in the committee charter, and make recommendations about study conduct to the NHLBI. As the Adult PASC Investigator Consortium study does not involve any interventions, an early stopping rule for efficacy or futility is not indicated.

11.2 Data Safety Monitoring Plan

The Data and Safety Monitoring Plan for this trial will follow recommended monitoring principles for an observational study of a vulnerable population. Oversight of data and safety is provided by the RECOVER Observational Safety Monitoring Board appointed by NHLBI. The OSMB will be composed of experts in longitudinal research (adult and pediatric populations), clinical experts in adult and pediatric manifestations of COVID-19, biostatistics, bioethics, and patient/caregiver representatives. The OSMB will also appoint ad hoc members with subspecialty expertise in the diverse array of clinical manifestations of PASC. The OSMB will meet at least twice a year to review data on AEs, adverse reactions, suspected adverse reactions, unanticipated events, patient-reported outcomes, data quality, and study recruitment, and make recommendations about study conduct to the NHLBI. As the PASC study does not involve any interventions, an early stopping rule for efficacy or futility is not indicated.

After each OSMB meeting, the OSMB determination letter and a summary report of adverse events will be prepared within 30 days and will be distributed by NHLBI staff to each principal investigator and study coordinator for review. The summary report will contain the following information:

- A statement that an OSMB review of outcome data, adverse events, and information relating to study performance across all centers took place on a given date.
- A statement as to whether or not the frequency of adverse events exceeded what was expected and indicated in the informed consent.
- A statement that a review of recent literature relevant to the research took place.
- The OSMB's recommendation with respect to progress or need for modification of the protocol or informed consent. If the OSMB recommends changes to the protocol or informed consent, the rationale for such changes and any relevant data will be provided.

• A statement that if safety concerns are identified, the NHLBI Program Official will communicate these promptly to the investigators.

12 Statistical Considerations

The analysis will integrate retrospective and prospective data on individuals at multiple stages, including pre-infection, acute infection, and long-term progression and recovery. Characterizing the incidence and prevalence of PASC will be achieved by estimating the incidence of PASC phenotypes among subjects with COVID-19 infection, compared with uninfected individuals followed over the same time.

To characterize the clinical course, recovery, and risk factors of PASC, PASC positive individuals will be compared with infected PASC negative individuals and uninfected individuals to characterize patterns. To define the pathophysiology and mechanisms of PASC, we will estimate the direct and indirect effects of COVID-19 infection and its severity on the development of PASC. Longitudinal data models such as generalized estimating equations, generalized linear mixed models, and functional principal component analysis will be used to characterize patterns of outcomes and develop analysis models.

12.1 Hypotheses to be Tested

The following hypotheses will be addressed in the analytic approach to Aim 1:

- Hypothesis 1a: Clinically meaningful PASC cases and sub-phenotypes will be discernable based on a combination of candidate PASC symptoms, and potentially other clinical features.
- Hypothesis 1b: Cumulative incidence of long-term sequelae differs between SARS-CoV-2 infected and uninfected individuals, overall and stratified by hospitalization.
- Hypothesis 1c: Incidence rate of long-term sequelae differs between SARS-CoV-2 infected and uninfected individuals, overall and stratified by hospitalization
- Hypothesis 1d: The point prevalence of long-term sequelae differs between SARS-CoV-2 infected and uninfected individuals, overall and stratified by hospitalization.
- Hypothesis 1e: The severity of long-term sequelae differs between SARS-CoV-2 infected and uninfected individuals, overall and stratified by hospitalization.

The following hypotheses will be addressed in the analytic approach to Aim 2:

- Hypothesis 2a: The risk of PASC among infected individuals will vary by: demographic and clinical characteristics, vaccine status at the time of infection, severity of disease (including hospitalization and admittance to ICU), drug exposures, pregnancy during acute infection and calendar time.
- Hypothesis 2b: The rate of recovery from PASC among individuals with PASC will vary by: (i)
 demographic and clinical characteristics and vaccine status at the time of infection, and (ii) severity
 of disease (including hospitalization and admittance to ICU), drug exposures, and pregnancy during
 acute infection.

The following hypotheses will be addressed in the analytic approach to Aim 3:

- Hypothesis 3a: PASC and PASC sub-phenotypes will be associated with concurrent and subsequent abnormal laboratory results and other clinical and subclinical features.
- Hypothesis 3b: The association between PASC and PASC sub-phenotypes with concurrent and subsequent abnormal laboratory results and other clinical and sub-clinical features will be modified by demographic factors, including sex, age and race/ethnicity.
- Hypothesis 3c: Recovery from PASC will be associated with laboratory results and other clinical and subclinical features.
- Hypothesis 3d: The association between SARS-CoV-2 infection and PASC and PASC subphenotypes will be mediated by abnormal laboratory results and other clinical and sub-clinical features.

12.2 Sample Size Determination

The following factors were considered in determining the sample size

- Expected frequency of PASC in the SARS-CoV-2 infected population. Population estimates from studies with selection bias currently range from 25-70%; we used 25% as a conservative estimate.
- The desire for the cohort distribution to include a diverse population, with overrepresentation from non-Hispanic Black, Hispanic and Asian populations relative to general population prevalence to account for a higher rate of SARS-CoV-2 infection and PASC in these populations
- The desire to be able to perform subgroup analyses based on characteristics such as age, sex, race/ethnicity, pregnancy, vaccination status and combinations thereof.

Table 7 shows minimal detectable effect sizes for the key study questions both for the full study sample (Tier 1 N=14,880; Tier 2 N=4,464 and Tier 3 N=2,976) and for subgroups of 25% thereof. These sample sizes for Tier 2 and Tier 3 assume that 25% of infected subjects will have abnormal symptoms. It is further assumed that all infected subjects with abnormal symptoms will progress to Tier 2 (N=3,050) and 5.6% of infected subjects without symptoms will progress to Tier 2 (N=512). Among uninfected subjects, 26.8% (N=718) will progress to Tier 2. 68% of infected subjects with abnormal symptoms will progress to Tier 3, and 3.8% of infected subjects without symptoms will progress to Tier 3. Among uninfected subjects, 18.2% will progress to Tier 3. The infected cohort is expected to include 1,867 pregnant individuals and the uninfected cohort is expected to include 583 pregnant individuals.

Table 7: Sample size calculations

					Min detectable ES*	
Tier	Comparison groups		Effect of interest	Assumptions	Full sample	25% subgroup (e.g. inpatients, Hispanic individuals, etc.)
1	Infected	Uninfected	Difference in risk of PASC between infected and uninfected	Risk of PASC in infected: 25%	3.50%	6.80%
1	Infected w/ RF	Infected w/out RF	Risk difference for PASC in infected with RF vs. without RF	Prevalence of RF: 20%, risk of PASC in infected, RF+: 30%	3.90%	7.60%
1	Pregnant infected	Non- pregnant infected	Risk difference for PASC in pregnant infected versus non- pregnant infected	Risk of PASC in non-pregnant infected: 25%	4.10%	8.00%
1	PASC+ w/ RF	PASC+ w/out RF	Difference in proportion who recover from PASC for those with and without a risk factor	Prevalence of RF: 20%, probability of recovery in PASC+ w/out RF: 0.50	8.70%	17.20%
2	PASC+		Precision of rate of feature	Rate of 50% (conservative)	± 2.3%	± 4.7%
2	Infected	Uninfected	Difference in proportion with a features in between infected	Rate of 50% with feature in infected	7.90%	15.60%

			and uninfected individuals			
2	PASC+	PASC-	Difference in proportion with a feature, PASC+ vs. PASC-, infected only	Rate of 50% with feature in PASC+ (conservative)	10.00%	19.70%
3	PASC+		Precision of rate of feature	Rate of 50% (conservative)	± 2.8%	± 5.7%
3	Infected	Uninfected	Difference in proportion with a feature, infected vs. uninfected	Rate of 50% in PASC+ (conservative)	9.50%	18.80%
3	PASC+	PASC-	Difference in proportion with a feature, PASC+ vs. PASC-	Rate of 50% in PASC+ (conservative)	12.10%	23.40%

Only infected participants are included in analyses that consider PASC+ alone, or compare PASC+ with PASC-.

*ES: effect size; RF: risk factor

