Objectives	 Characterize the incidence and prevalence of sequelae of SARS-CoV-2 infection. Characterize the spectrum of clinical symptoms, subclinical organ dysfunction, natural history, and distinct phenotypes identified as sequelae of SARS-CoV-2 infection. Define the biological mechanisms underlying pathogenesis of the sequelae of SARS-CoV-2 infection. 	
Methodology	Ambi-directional longitudinal meta-cohort study (combined retrospective and prospective) with nested case-control studies.	
Endpoint	Primary Endpoints: Presence of candidate PASC symptoms over time (incidence and prevalence). Secondary Endpoints: Biological and recovery trajectories from SARS-CoV-2 infection; organ injury; incident clinical disease.	
Study Duration	Four years	
Subject Duration	Up to four years	

Title	NIH RECOVER: A Multi-site Observational Study of Post-Acute Sequelae of SARS-CoV-2 Infection in Adults	
Population	Infected: Individuals at least 18 years of age meet WHO criteria for suspected, probable or confirmed SARS-CoV-2 infection on or after January 1, 2020.	
	Uninfected: Individuals at least 18 years of age who have never met any of the WHO criteria for suspected, probable or confirmed SARS-CoV-2 infection.	
Number of subjects	12,200 total subjects with SARS-CoV-2 infection and 2,680 total subjects without SARS-CoV-2 infection.	
Statistical Analysis	A flexible study design is proposed to allow modifications to PASC case definition, tiered phenotyping assessments, comparator groups, and/or statistical plan after its initiation to optimize public health impact without undermining validity and integrity of study findings. Modifications in study design may be based on analyses of structured cohort data, unstructured cohort EHR data, and other cohort EHR data.	

2 Key Roles

Principal Investigators Clinical Science Core [name] MS
Helen L. and Martin S. Kimmel Professor of
Advanced Cardiac Therapeutics
Director Heart Failure Programs
NYU Grossman School of Medicine
Leon H. Charney Division of Cardiology
[name]
New York, NY 10016
[contact]

[name]
Professor and Director, Division of Biostatistics
Department of Population Health
NYU Grossman School of Medicine
[name]
New York, NY 10016
[contact]

[name], MHS
Professor, Department of Population Health at
NYU Grossman School of Medicine
Professor, Department of Medicine at NYU
Grossman School of Medicine
Director, Center for Healthcare Innovation and
Delivery Science

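### Section 12.2 calls the 25% PASC frequency conservative without limit, but for the Tier 1 absolute risk differences it is the most favourable value in the cited 25-70% range

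*Protocol*

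**What the plan says.** The first factor listed in section 12.2 is the expected frequency of PASC among infected people. The text reads: "Population estimates from studies with selection bias currently range from 25-70%; we used 25% as a conservative estimate". Nothing limits the word to particular calculations.

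Table 7 then gives minimal detectable differences for the full sample and for a 25% subgroup. The first three Tier 1 rows are absolute differences in PASC risk:

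- Row 1, infected versus uninfected: assumption "Risk of PASC in infected: 25" per cent; 3.50% and 6.80%.
- Row 2, infected with versus without a risk factor (RF): assumption "Prevalence of RF: 20%, risk of PASC in infected, RF+: 30" per cent; 3.90% and 7.60%.
- Row 3, pregnant versus non-pregnant infected: assumption "Risk of PASC in non-pregnant infected: 25" per cent; 4.10% and 8.00%.

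No detectable difference is shown at any other PASC risk. Five of the six Tier 2 and Tier 3 rows label a 50% feature rate as conservative; the PASC+ precision rows, for example, carry "Rate of 50% (conservative". The 25% frequency also fixes the number of infected participants with symptoms (3,050), which feeds the recovery row and Tiers 2 and 3.

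**The concern.** A planning value is conservative if other plausible values would give an equal or better result. For a difference between two proportions, the assumed risk enters mainly through the binomial variance p(1-p), which is largest at 50%. Of all values from 25% to 70%, 25% gives the smallest variance and hence the smallest detectable difference. The same table uses the word in the correct sense for feature rates, where 50% is the worst case. Section 12.2 therefore uses one word in opposite directions for the same kind of calculation.

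Row 1 is the contrast behind the hypotheses that cumulative incidence and point prevalence differ by infection status (1b and 1d in section 12.1). Rows 2 and 3 serve the risk-factor hypothesis 2a. A reader who takes 25% as conservative would expect the study to do at least as well as these rows if PASC proves more frequent. Across the cited range it would do somewhat worse.

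**Working it through.** **Inputs**

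- Row 1: the Protocol Summary gives "12,200 total subjects with SARS-CoV-2 infection and 2,680 total subjects without SARS-CoV-2 infection".
- Row 2: 20% of 12,200 = 2,440 with the risk factor, 9,760 without.
- Row 3: section 12.2 says "The infected cohort is expected to include 1,867 pregnant individuals", leaving 12,200 − 1,867 = 10,333 non-pregnant.
- Alpha and power: not printed in the protocol, so inferred by matching Table 7.

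**Formula.** Two-proportion z test with pooled variance under the null and the comparator risk p2 below the stated risk p1. Solve for d = p1 − p2 in

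d = z(1−α/2)·√[p̄(1−p̄)(1/n1 + 1/n2)] + z(power)·√[p1(1−p1)/n1 + p2(1−p2)/n2],

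where p̄ is the weighted mean risk.

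**Reproducing Table 7.** Take two-sided α = 0.01 (z = 2.576) and 90% power (z = 1.282). For row 1 at p1 = 0.25 and d = 0.0349, p2 = 0.2151 and p̄ = 0.2437. The two standard errors are 0.00916 and 0.00885, so 2.576 × 0.00916 + 1.282 × 0.00885 = 0.0236 + 0.0113 = 0.0349. The other rows agree as well:

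| Row | Printed (full / 25% subgroup) | Computed |
|---|---|---|
| 1 | 3.50 / 6.80 | 3.49 / 6.84 |
| 2 | 3.90 / 7.60 | 3.90 / 7.59 |
| 3 | 4.10 / 8.00 | 4.10 / 8.00 |
| Recovery (2,440 v 610) | 8.70 / 17.20 | 8.69 / 17.15 |

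Alpha 0.05 with 80% power gives 2.55, 2.85 and 3.00 for rows 1 to 3, which does not match.

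**Variance over the cited range.** 0.25 × 0.75 = 0.1875; 0.50 × 0.50 = 0.25; 0.70 × 0.30 = 0.21.

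**Detectable difference (%), full sample / 25% subgroup, by the reference risk** (RF+ risk in row 2)

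| Row | 25% | 30% | 50% | 70% |
|---|---|---|---|---|
| 1 | 3.49 / 6.84 | 3.71 / 7.30 | 4.11 / 8.20 | 3.82 / 7.73 |
| 2 | 3.66 / 7.06 | 3.90 / 7.59 | 4.36 / 8.67 | 4.09 / 8.31 |
| 3 | 4.10 / 8.00 | 4.37 / 8.55 | 4.84 / 9.65 | 4.51 / 9.13 |

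On a one-point grid from 25% to 70%, the minimum is at 25% in every row and the maximum is just above 50%. For the full sample, the values at 50% equal these maxima to within 0.01 points.

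**Inflation from the printed basis to 50%.** Row 1: 4.11/3.49 = 1.18. Row 2: 4.36/3.90 = 1.12. Row 3: 4.84/4.10 = 1.18. At alpha 0.05 and 80% power the ratios are 1.17, 1.11 and 1.17.

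**Power at the printed full-sample differences, alpha 0.01.** At a 50% risk it falls from 90% to 76%, 81% and 75% (rows 1 to 3). At 70% it is 83%, 87% and 83%.

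**Where the label is right.** In the recovery row, a higher PASC frequency adds participants: 8.69% at 25% PASC (3,050 people), 6.16% at 50% (6,100) and 5.21% at 70% (8,540). There 25% is the least favourable value in the range.

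**The case against.** The word is attached to the expected frequency of PASC, not to rows 1 to 3, which only list their assumptions. Read as a low-end frequency from biased studies, 25% is a reasonable choice, and it is conservative wherever it sets counts. This stands. The fault is that the label has no stated scope, not that 25% is a bad planning value.

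The range is itself discounted, since the protocol attributes it to studies with selection bias. Below 25% the detectable differences shrink further: row 1 is 3.21% at 20% and 2.84% at 15%. So 25% is a minimum only within 25-70%. But this also shows that a lower risk is the easier case for these rows, so it does not make 25% conservative for them.

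The power losses depend on the inferred alpha. At two-sided alpha 0.05 and a 50% risk, power at the printed 3.5%, 3.9% and 4.1% is still 91%, 93% and 90%. This stands, and the power figures are conditional. Section 12.4 also provides for monitoring PASC frequency and altering recruitment if it departs from plan. That lessens the consequence but does not restate Table 7.

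Three stronger readings are tempting, and the documents support none of them:

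- *Table 7 is miscalculated.* It is not; the four Tier 1 rows reproduce from their stated inputs to within 0.05 points.
- *All three rows are the best case at 25%.* Row 2 assumes 30% in RF+. Its minimum is 3.66%, so 3.9% lies about a third of the way to its 4.36% maximum: (3.90 − 3.66)/(4.36 − 3.66) = 0.34.
- *The cohort is too small, or 25% must be replaced by 50%.* The change is at most about 0.7 points in the full sample and 1.7 in a 25% subgroup. Nothing in the protocol says 50% is the expected PASC risk.

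**Conclusion.** The concern holds as a point about the scope of one word and the range shown. Section 12.2 attaches a property to the 25% input that is true for quantities driven by the PASC+ count and false for the Tier 1 absolute risk differences. Within 25-70%, rows 1 and 3 show their most favourable values and row 2 is near that end. The worst case is about 0.6 points higher in row 1 (3.5% to 4.1%), 0.5 in row 2 (3.9% to 4.4%) and 0.7 in row 3 (4.1% to 4.8%).

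That 25% is lowest and about 50% highest does not rest on the inferred alpha and power, and the relative inflation hardly changes with them. The exact differences and the power figures do rest on them. The effect is modest and does not undermine the sample size, but it touches the main infected-versus-uninfected contrast and is worth correcting.

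**What to change.** In section 12.2, limit the word conservative to the rows that depend on the number of PASC+ participants: the Tier 1 recovery row and the Tier 2 and 3 PASC+ rows. Keep 25% as the planning value there.

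In Table 7, show rows 1 to 3 over the cited 25-70% range, or keep the existing figures and add the 50% case beside them. On the inferred alpha and power, the 50% figures (full sample / 25% subgroup) are about 4.1%/8.2%, 4.4%/8.7% and 4.8%/9.7%. At 70% they are about 3.8%/7.7%, 4.1%/8.3% and 4.5%/9.1%. The study team should recompute them with its own alpha and power. Replacing 25% outright with 50% in these rows would be a preference and is not needed.

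The cost is one sentence and three table rows. Enrolment and design do not change; the stated limits become slightly less favourable.

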All relevant symptoms are described in the corresponding procedure's SOP. As the symptoms that are most relevant to PASC are better understood, RECOVER's subject matter experts refine the list of relevant symptoms for each test. Once the target sample size (see Section 12.2) has been reached with adequate data quality within each bucket, we cease assigning the test to people in that bucket. This ensures that our total enrollment and procedure sample sizes are as small as can be in order to ensure usable data. In other words, this approach allows us to minimize the number of people that we ask to undergo each test and the risk of the study, while maintaining adequate statistical power.

We anticipate that approximately 30% of participants will undergo each Tier 2 test and a maximum of 20% of participants will undergo each Tier 3 test. For Tier 2 testing, a random sample of 5.6% of SARS-CoV-2 infected and 11.4% of uninfected participants will be asked to undergo each Tier 2 test. These percentages may be modified to ensure the correct distribution of PASC and control participants as testing accrues. In addition, some or all participants who meet test-specific clinical criteria set by subject matter experts will be offered the test so that we ensure an adequate number of participants likely to have a positive test for statistical analysis (see Appendix 5: Tier 2 and 3 eligibility, exclusion criteria for additional description of this process). Among the eligible participants, REDCap will assign some or all of those that meet clinical oversample eligibility criteria to the test (at adaptive proportions designed to keep the total number of participants assigned to the test at not more than 30%) and will randomly assign the test to some of the remainder as described above. As RECOVER follows an adaptive study design, the relevant symptoms for each test will be reviewed and updated periodically to ensure the proper proportion and populations are being selected. When relevant symptoms are changed for tests that also allow random assignment, they only affect the proportion of participants with various conditions assigned the test, but do not change the fact that any participant is still eligible and therefore do not change the risk of the study as a whole. Any participant may decline any Tier 2 or Tier 3 test if offered.

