(C-SSRS, MINI, PCL-5, PG-13-R)		ANY of the following: Positive suicidality screener Positive depression screener Positive anxiety screener Positive PTSD screener Experiencing persistent grief		patient has been assessed by a clinician to not be at elevated risk of harm. If the C-SSRS is positive for medium or high risk, the participant must meet with the site's medical or mental health professional prior to conducting the MINI to determine appropriateness of the interview. Should the clinician determine the MINI to be inappropriate due to severity of symptoms, it should be rescheduled at a later time. The main risk of concern is suicidal thinking and urges.
Vision testing	2	All participants are eligible for this test through random assignment. Participants with relevant symptoms (as outlined in the applicable SOP) will be oversampled for assignment as follows: ALL of the following: Reduced visual functioning	N/A	N/A
UPSIT	2	All participants are eligible for this test through random assignment. Participants with relevant symptoms (as outlined in the applicable SOP) will be oversampled for assignment as follows: ALL of the following: Altered smell and/or taste	N/A	N/A
NIH Toolbox	2	All participants are eligible for this test through random assignment. Participants with relevant symptoms (as outlined in the applicable SOP) will be oversampled for assignment as follows:	N/A	Permissible clinical variation:

Procedure name(s)	Tier	Eligibility	Exclusion criteria	Additional information about test procedures and permissible clinical variation
		ALL of the following: Reduced cognitive functioning		Specific components may be performed remotely if no option for in person testing
		All participants are eligible for this test through random assignment. Participants with relevant symptoms (as outlined in the applicable SOP) will be oversampled for assignment as follows:		
ACTH	2	 Post-exertional malaise Anorexia hydr meth 	Systemic glucocorticoids (e.g. hydrocortisone, prednisone, methylprednisolone, dexamethasone)	N/A

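### Table 7's PASC+ precision (±2.3% Tier 2, ±2.8% Tier 3) is a best case: it counts PASC+ as the group tested, but each test is assigned by its own relevant symptoms

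*Protocol*

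**What the plan says.** The Protocol Summary gives "12,200 total subjects with SARS-CoV-2 infection and 2,680 total subjects without SARS-CoV-2 infection". Section 12.2 uses the 25% figure twice. For the frequency of PASC among infected people, "we used 25% as a conservative estimate"; for progression to the higher tiers, it assumes that "25% of infected subjects will have abnormal symptoms". Both give 3,050 people. Section 12.2 then continues: "It is further assumed that all infected subjects with abnormal symptoms will progress to Tier 2 (N=3,050"), that 5.6% of infected participants without symptoms join them, and that the Tier 3 shares are 68% and 3.8%.

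Table 7 has one row per tier headed "Precision of rate of feature" for PASC+, at an assumed rate of 50%. The full-sample entries are ±2.3% and ±2.8%, and the 25% subgroup entries are ±4.7% and ±5.7%. No confidence level is given.

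Section 6.1 describes assignment test by test. Its Table 2 sorts participants into four buckets by infection status and symptoms relevant to the test, with Bucket 1 being infected with relevant symptoms. It says that "some or all participants who meet test-specific clinical criteria set by subject matter experts will be offered the test", adds a random sample (5.6% of infected for Tier 2), allows the percentages to change as testing accrues, and allows anyone to decline. A test is no longer assigned within a bucket once that bucket's Section 12.2 target is met. Appendix 5 lists the triggers. For the smell test (UPSIT) the trigger is "Altered smell and/or taste"; for chest CT or pulmonary function tests it is any one of a broad list.

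**The concern.** Section 12.2 treats PASC+ as the group that is tested. Section 6.1 and Appendix 5 make the tested group those with one test's own symptoms or findings. A PASC+ participant without that trigger reaches the test only through the random sample and, for some tests, not at all. The PASC+ row of Table 7 and Bucket 1 of Section 6.1 are then different populations that share one planning count.

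Two things are at stake. A reader will take ±2.3% and ±2.8% as the precision with which a feature can be estimated in people with PASC, for any Tier 2 or Tier 3 test. In addition, Section 6.1 stops assigning a test when the Section 12.2 target is reached in a bucket, so an unclear definition of the counted group makes that target unclear too.

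**Working it through.** **Inputs from the protocol.** Infected 12,200; symptomatic share 25%; Tier 3 share of symptomatic 68%; feature rate p=0.5; random rate 5.6% (Tier 2) and 3.8% (Tier 3) in infected participants without symptoms; at most 20% of participants per Tier 3 test. Counts: 0.25 × 12,200 = 3,050, and 0.68 × 3,050 = 2,074 (the latter is not printed).

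**Reproducing Table 7.** Half-width = z × √(0.25/n).

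| Row | n | 95% (z=1.960) | 99% (z=2.576) | Stated |
|---|---|---|---|---|
| Tier 2 | 3,050 | ±1.77% | ±2.33% | ±2.3% |
| Tier 2, 25% subgroup | 762.5 | ±3.55% | ±4.66% | ±4.7% |
| Tier 3 | 2,074 | ±2.15% | ±2.83% | ±2.8% |
| Tier 3, 25% subgroup | 518.5 | ±4.30% | ±5.66% | ±5.7% |

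All four entries match at 99% and none at 95%. The 99% level is an inference. It is supported by six of the eight two-group rows of Table 7, whose full-sample entries reproduce at two-sided alpha 0.01 with 90% power.

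**How much slack there is.** To stay at the stated figures after rounding (below 2.35 and 2.85 points) at 99%, n must be at least 3,004 and 2,042. Each is 98.5% of the count used.

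**Cases that need no assumed symptom share.**
- *EndoPAT (Tier 3).* Appendix 5 lists random assignment only, at sites with the equipment, with no symptom oversample. At the 20% ceiling, 0.20 × 3,050 = 610 PASC+ are tested: 2.576 × √(0.25/610) = ±5.2%. Even if all 2,976 Tier 3 places went to infected participants, the rate would be 2,976/12,200 = 24.4%, giving about 744 PASC+ and ±4.7%.
- *Criteria-only tests.* Appendix 5 restricts EMG, nerve conduction, muscle biopsy, invasive CPET and right heart catheterization to participants who meet criteria. PASC+ participants outside the criteria have no chance of being tested, so no sample size or weighting gives a rate for PASC+ as a whole.

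**Illustration for the other tests.** Let f be the share of PASC+ who meet a test's criteria. The protocol does not give it, so these values are assumptions. For Tier 2, with all who qualify tested and the 5.6% rate kept:
- n = 3,050 × [f + 0.056(1−f)]
- Unweighted half-width = 2.576 × √(0.25/n)
- Half-width weighted to all PASC+ = 2.576 × √(0.25/3,050) × √[f + (1−f)/0.056]

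| f | n tested | Unweighted, 99% | Weighted to all PASC+, 99% |
|---|---|---|---|
| 0.90 | 2,762 | ±2.45% | ±3.8% |
| 0.75 | 2,330 | ±2.67% | ±5.3% |
| 0.50 | 1,610 | ±3.21% | ±7.2% |

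For Tier 3 the result depends on how the 68% is read. If 68% of those who qualify plus 3.8% of the rest are tested, f=0.75 gives n=1,584 and ±3.24%, and f=0.50 gives n=1,095 and ±3.89%. If all who qualify plus 3.8% of the rest are tested, up to 2,074, f=0.75 gives ±2.83% and f=0.50 gives n=1,583 and ±3.24%. These are unweighted.

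**The Bucket 1 reading.** If 3,050 is a per-test target for infected participants with that test's symptoms, it can be reached where at least 3,050/12,200 = 25% of infected qualify and are tested. The ±2.3% then holds, but for Bucket 1.

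**The case against.** The best defence is that Section 6.1 plans numbers per test. It expects about 30% of participants in each Tier 2 test, ties assignment to the Section 12.2 targets by bucket, and lets the proportions adapt. On that reading 3,050 is a Bucket 1 target that can be met for many tests. The illustration above holds the 5.6% rate fixed and so lets the total fall: at f=0.50 the test would have 1,610 + 512 + 718 = 2,840 participants, or 19% of 14,880. Many triggers are broad any-of lists, for which f may be high. The 25% PASC frequency is itself described as conservative, and a higher frequency would raise the count. Finally, if the intervals were meant at 95%, ±2.3% and ±2.8% would need only about 1,815 and 1,225 people.

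Much of this stands. A reader might infer that the stated precision fails for every test. The documents do not support that: the symptom share is not given, the loss for broad triggers may be small in the unweighted figure, and Tier 3 can still reach 2,074 if about two thirds of PASC+ qualify and all are tested. A reader might also infer that PASC+ feature rates will be reported unweighted and therefore biased. The protocol does not say so; Section 12.5 leaves the analysis to a separate SAP, which was not available here.

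The defence does not rescue the label. The Bucket 1 reading makes the row a statement about Bucket 1, not PASC+. The 95% reading does not reproduce Table 7 from the stated counts, and it leaves EndoPAT short, since 744 is below 1,225. Neither reading helps the criteria-only tests.

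**Conclusion.** The concern holds in a limited form. The arithmetic of the PASC+ precision rows is sound at 99% for n=3,050 and n=2,074. The fault is that these counts are labelled PASC+ while the design fills each test by test-specific symptoms. For PASC+ as a whole the figures are a best case that requires about 98.5% of the counted participants to take the test. Otherwise they can describe only Bucket 1, where enough infected participants qualify (about 25% for Tier 2).

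Two results do not rest on an assumed symptom share. EndoPAT gives about ±5.2% against ±2.8%, assuming random assignment at an equal rate up to the 20% ceiling, and criteria-only tests cannot yield a PASC+ rate at all. The Tier 2 range, about ±3.2% to ±2.5% unweighted or ±7.2% to ±3.8% weighted, is only an illustration. It assumes f between 50% and 90%, a fixed 5.6% random rate, full uptake and a 99% level.

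**What to change.** In Table 7, relabel the two PASC+ precision rows as infected participants with the test's relevant symptoms (Bucket 1), and state the confidence level. Give expected counts and precision per test, or over a range of symptom shares. If PASC+ as a whole is meant, restate the precision allowing for the different sampling fractions of those with and without the test's symptoms. Mark the criteria-only tests as estimating the symptomatic subgroup only, and give EndoPAT its own figure. Say in Section 12.2 which bucket each target refers to, so that the rule in Section 6.1 for ceasing assignment has a defined count.

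The cost is a revised table and a few sentences, with no change to procedures or enrolment. The downside is less favourable stated precision.
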